8.3 Key Inclusion Criteria

Eligibility Criteria: Men and women ≥ 18 yrs. of age who are full-time or part-time employees at SEPTA, IBC, or the City of Philadelphia; who have a BMI of 30 to 55 kg/m². (the upper limit of BMI will minimize the influence of outliers on the main result of weight loss). Participants must also have at least one other cardiovascular risk factor (high blood pressure, hypercholesterolemia, diabetes, smoking), which will be obtained by self-report. Participants must receive their health benefits from Independence Blue Cross; one of our partners in the study.

8.4 Key Exclusion Criteria

Exclusion criteria will be limited to factors that may confound results or that make participation in a weight loss program unfeasible, unsafe, or require more intensive monitoring, as detailed in our prior work. These exclusions include: unstable heart disease, uncontrolled hypertension, kidney disease, and other serious chronic illness (e.g., transplant recipient, terminal illness); substance abuse; bulimia nervosa or related behaviors; or diabetes medication other than metformin; pregnancy or breast feeding; contraindications to counseling about diet, physical activity, or weight reduction; unstable mental illness. Participants with diabetes on medications besides metformin are excluded because these medications may require adjustment during weight loss to prevent hypoglycemia and dehydration. Individuals unable to read consent forms or fill out surveys in English will be excluded.

9. Subject Recruitment

9.1 Target Population

For this study we are collaborating with 3 important community partners in Philadelphia: SEPTA (which runs public transit in Philadelphia); IBC, the region's largest insurer; and the City of Philadelphia, the largest employer in Philadelphia. Each of these entities has a large number of employees (9,200 SEPTA; 4,500 IBC; and 5,300 City of Philadelphia) with a high degree of obesity (estimated 55% SEPTA, 36% IBC, 42% City); and a high proportion of African Americans (56.6% SEPTA, 38.4% IBC, 50% City). Eligible participants will be men and women above age 18 who are full-time or part-time employees at SEPTA, IBC, or the City of Philadelphia who have a BMI of ≥ 30 to ≤ 55 kg/m². Participants must also have at least one other cardiovascular risk factor (high blood pressure, hypercholesterolemia, diabetes, smoking), which will be obtained by self report.

9.2 Accrual

There are an estimated 4,800 employees from the Southeastern Pennsylvania Transportation Authority (SEPTA), Independence Blue Cross (IBC), and the City of Philadelphia who have BMI greater than 30 and 1 or more cardiovascular risk factor, of whom approximately 48% are black. We plan to enroll 344 participants over 6 months making our recruitment targets easily attainable given the size of the recruitment pool.

9.3 Subject Recruitment

With assistance from IBC, SEPTA, and the City Department of Public health, we will advertise this as a research study of different ways to help people lose and keep off weight. The initial outreach to employees will be facilitated by IBC, SEPTA, and the City of Philadelphia, utilizing their existing communication channels (e.g. letter mailings, email, text, intranet, flyers, posters, digital display in the workplace). All recruitment materials will be submitted to the IRB before any study activities occur.

Interested participants will be asked to go to the Way to Health (WTH) website for prescreening and eligibility ascertainment. The screening intake form will be completed using the WTH website supplemented by phone support as needed. In order to verify BMI eligibility for the study, a verified in-person weight measurement will be required during the screening process.

Recruitment at Independence Blue Cross site (IBC):

After initial outreach by IBC's communication channels, individuals will be asked go to the Way to Health (WTH) website for prescreening and eligibility ascertainment. In collaboration with IBC, the research study team will have a table set up at the IBC site during their annual biometric screening event. For IBC employees who previously completed online pre-screening and consent, the research staff will obtain individuals' weight measurement from their biometric screening. For IBC employees who did not complete the online pre-screening and consent prior to the biometric screening event, verbal consent will be obtained (similar to phone screening) to record their weight measurement from the biometric screening in order to determine BMI eligibility for the study.

For IBC employees who are interested in the study but did not attend the biometric screening event, in-person weight measurements will be obtained on site by the Fitness Director at IBC's MediFit Fitness Center. For these IBC employees, informed consent will have been obtained (online) in advance of the in-person weight measurements. Specific language is outlined in the consent form reflecting this method of in-person weight measurements for IBC employees. Individuals weight data will be transferred to the research team via SecureShare; a web-based application used by the University of Pennsylvania for secure file exchange

Recruitment at SEPTA site:

After initial outreach by SEPTA's communication channels, individuals will be asked go to the Way to Health (WTH) website for prescreening and eligibility ascertainment. In-person weight measurements will then be obtained at the SEPTA medical department by the research study staff, and also by the SEPTA nurse. The SEPTA nurse is also the main point-of-contact working with the research team for this study. The SEPTA nurse will obtain in-person weight measurements only on an as needed basis in the event research staff is not available to be on-site.

In-person weight measurements at the City of Philadelphia (CoP) site:

After initial outreach by the City of Philadelphia's communication channels, individuals will be asked go to the Way to Health (WTH) website for prescreening and eligibility ascertainment. In-person weight measurements will then be obtained at the CoP site by the research study staff.

9.4 Subject Compensation

To enhance retention, we will provide participants a total of \$250 for completing follow-up visits. Participants will receive \$50 for completing weights at the screening baseline visit and at follow-up visits at 6, 12, 18, and 24 months regardless of weight. This strategy has minimized differential drop out in our previous studies. (For the lottery incentive payments, please refer to the 'Design of the Incentives' header in the Procedures section of this application)

10. Study Procedures

Consent Process

10.1 Overview

Upon the initial outreach, individuals who are interested in learning more about the study will be directed to the Way to Health web portal. Upon reaching the portal, participants will complete a

screening intake form to determine their eligibility. If participants are interested in participating, the Way to Health portal will take them through an automated online written informed consent session. The consent session will be divided into sections and potential participants will have to click a button to advance through each section. This is to help ensure that participants read the consent form thoroughly by breaking down the form into manageable blocks of text. Each section will have a button allowing the user to contact a researcher via email if she has questions about the consent form. Successive screens will explain the voluntary nature of the study, the risks and benefits of participation, alternatives to participation, and that participants can cease to participate in the study at any time. On the final consent screen, potential participants who click a clearly delineated button stating that they agree to participate in the study will be considered to have consented to enroll. Participants will then be randomized to one of the four arms by the web application. The participant will be led through an automated description of the details specific to that arm. After receiving such information, participants will be asked to confirm that they understand and wish to continue. Participants will be able to contact the research staff if they have any questions about their assigned condition before they proceed to the next step. Participants will be provided with details regarding how to contact the research team via email or phone at any time if they subsequently wish to withdraw from the study. This contact information will remain easily accessible via the subjects individual Way to Health web portal dashboards throughout the study.

Procedures

10.2 Baseline pre-treatment assessment for patients

Individuals who meet study entry criteria and have provided consent online will complete an intake survey measuring their health history, dietary intake, exercise habits, and previous weight loss efforts, and selected psychosocial variables shown to predict weight loss participation and success.

10.3 Randomization

Randomization: Study participants at study inception are randomized through the Way to Health Platform using a random number generator and permuted block randomization with variable block sizes to force balance among treatment group assignments; variable block sizes will preclude prediction of treatment assignments by study staff. Randomization will be in a 1:1 ratio for each intervention compared to control and will be stratified by: (1) the employer site; (2) sex, and (3) degree of obesity at baseline (BMI 30-37.9 and 38-55 kg/m²), as baseline BMI may moderate treatment effects. Following randomization, the study coordinator will provide instructions about the control, incentive, or environmental arms.

10.4 Environmental Change Strategies

The environmental change strategy arm will involve a menu of promising or evidence-based environmental change strategies to promote healthy eating and physical activity, delivered through print, website-based and mobile communication channels to employees assigned to the Environmental and Combined arms of the trial. The strategies have been identified through systematic literature

reviews, through [name] previous intervention studies, and from discussions with collaborators working on novel environmental change strategies. The planned environmental change strategies are based on our preliminary assessment and discussions with the participating worksite informants during the development of this proposal and are circumscribed by the context of these urban worksites and the structure of their employees work activities. The interventions are targeted at individual employees rather than work groups, due to the inclusion criteria (i.e., obese employees with at least one other CVD risk factor), feasibility considerations (individual rather than group randomization, total resources available), and the potential for translation, scalability and dissemination. As in many urban worksites, there are no in-house cafeterias but employees have access to lunchrooms for limited food and beverage preparation and storage (refrigerators, microwave ovens, vending machines) and are located near numerous food sources (restaurants, quick-serve or fast-food restaurants, lunch trucks, snack bars). Also, these worksites do not have fitness facilities on-site but have ample access to stairways, neighborhood gyms, and walking routes and parks within a 5-10 minute walk of their worksites.

Healthy eating environmental change strategies will be designed to guide participants in identifying environmental influences on excess food intake and making environmental modifications easier for them to implement in their worksites, in the area around worksites, and in their homes. At the worksite, the strategies will emphasize identifying healthy vending options, healthy snack access, social environment change, and establishing healthy catering policies for work-based events. In the neighborhood near the worksite, strategies will include tools to help workers find healthy choices easily at restaurants and periodic promotions (arranged with vendors) to encourage trying new healthful prepared foods. Home environment changes will be guided by the Home Food and Activity Environment Audit tool, originally developed for research conducted by [name] and colleagues at the Emory Prevention Research Center and recently adapted for an urban, low-income community intervention. Physical activity environment change strategies will also include strategies for worksites, near worksites, and in homes. At the worksites, strategies will include individually-delivered prompts to use stairs, standing desks, and walking breaks. In the area near worksites, strategies will include guidance on safe, convenient walking routes, link to benefits for incentives toward gym memberships, and safe bicycling paths. The Home Food and Activity Environment Audit will address physical activity environments in homes. Environmental strategies will be communicated to participants in the Environmental and Combined study arms twice weekly during the first 6 months, and weekly during months 7-18.

They will be varied to maintain interest and offer a variety of approaches that participants can use. The Way to Health platform will be programmed to send links to web and mobile intervention information, and to prompt participants who wish to have hard copy/paper copies of intervention materials. One week after a strategy tool is distributed, a simple log will be provided for participants to indicate their liking for, and use of, the various strategies. All participants in each of the three intervention arms will also receive a free wireless scale (value \$110) as this will be used to both obtain weights and provide participants with feedback. We are not providing these scales to participants in the usual care arm because that would not be consistent with usual care. Usual care: Employees of IBC, SEPTA, and City of Philadelphia are all offered the same wellness program that consists of: (1) yearly biometric screenings

for which members receive incentives to participate; (2) reimbursements for fitness and weight management program participation (up to \$150 per year for documentation of 120 workouts and up to \$150 for documentation of participation in Weight Watchers); (3) Eat Right for Life educational program which includes onsite seminar and workshop materials; (4) six visits with a registered dietician as part of health benefit; (5) free use of WebMD tools - members biometric data is uploaded or self-reported and tools are available to the member to set goals and track progress.

Psychological research has identified social support as a factor that can help support weight loss. In an effort to strengthen the social support environment for participants in the environmental strategies and the combined incentives and environmental strategies arms, we will create a “secret” Facebook group where participants in these arms will be encouraged to provide support and seek support from one another. We will encourage wall posts of text, healthy recipes, pictures related to nutrition, physical activity and the environment. The research study team will periodically post helpful links or tips that participants can use to improve their nutrition and physical activity environment.

Language added to the original informed consent document informs participants that we will ask participants assigned to some arms (who wish to join a voluntary Facebook group) to provide us with their Facebook e-mail address. Participants will be asked to provide us with their Facebook e-mail address by completing a single question survey on their personal account page on the Way to Health platform. Preceding the survey will be a Facebook addendum to the consent explaining more in depth details of participation in the Facebook group. Participants will be informed here that they can view and print a version of the Facebook addendum from their personal Healthy Weigh account page at any time. This form will also direct participants to view the “study instructions” section of their dashboard content for more specific information on how to locate one’s Facebook e-mail address, how to create a Facebook account, and how to accept our Facebook invitation. If participants do not have a Facebook profile, or choose not to provide us with this information, they may still participate in the study. This will be notated in the Way to Health dashboard content and on the Facebook addendum. We will invite participants in the environmental strategies arms to join the group called “Healthy Weigh,” via the Facebook e-mail address that they provide through the single question survey. Participant identity will only be revealed to other enrolled subjects in the environmental strategies arms if a participant decides to join the Facebook group. If a participant declines, they will remain anonymous.

The privacy type for the group will be “Secret.” This means that only research staff will have control over who joins the group. Only current or former group members, people who were in the group but left, can see the group’s name. No one outside of the study will be able to locate, view or join the group without an invitation from the study team. Only current members can see who else is in the group. Only current and former members can see group activity. Only current members can post in the group. Only current and former members will be able to find the group in a search. Only current members can see stories about the group on Facebook (in the News Feed and search).

The research study team will closely monitor Facebook group activity in order to ensure that all activity occurring with the group is appropriate and related to the study. If an inappropriate post is made the research study team will promptly remove the post, and will contact the participant who made the post

to review the purpose of the group and to review with the participant which types of posts are appropriate for the purposes of the research study. Inappropriate posts are any posts that do not relate to weight loss, social support, nutrition, physical activity, or the environment.

We intend to analyze the Facebook activity of participants within the Facebook group in order to determine: how many and which participants opt to join the group; how many posts, likes, and comments each participant makes during the study period; and whether the amount or nature of Facebook group activity corresponds with weight loss success. We also plan to look qualitatively at the nature of the posts, likes and comments of participants. No data analysis will be conducted until the end of the intervention. Data will be transcribed directly from Facebook into an excel sheet for tracking and organization of participant activity. This task will be completed by the research study personnel. The excel sheet will be stored in a password protected file on the secure/firewall servers of the PMACS Data Center, in data files that will be protected by multiple password layers. These data servers are maintained in a guarded facility behind several locked doors, with very limited physical access rights. An additional amendment will be forthcoming, which will explain the detailed data analysis process.

10.5 Outcome assessments

Weight for all participants will be ascertained in-person upon enrollment into the study and then at the visits at the end of Phase I (6 months), at 12 and 18 months (end of Phase II), and at 24 months (end of Phase III). The primary outcome will be change in the in-person weight from baseline to 18 months. We will utilize other measures collected at months 6, 12, 18 and 24 as part of routine biometric assessments by the participants' employers, all of whom share the same insurance carrier, Independence Blue Cross (IBC). The allowable visit windows for these weight milestones are: -2/+4 weeks for the 6 month visit, -2/+6 weeks for the 12 and 18 month visits, and -2/+8 weeks for the 24 month visit.

10.6 Design of the Incentives

The incentive programs incorporate key aspects of optimal design, including objective and reliable confirmation of behavior change at specified intervals (weight measurement), reinforcement of the target behavior (weight maintenance) with non-drug reinforcers (incentives), large payments to reinforce the target behavior, and intermittent reinforcement. All incentive participants will receive daily feedback for 18 months; they will be given an electronic scale (accurate to ± 0.2 lbs) and given a weight loss goal for the first 6 months of 0.5 lb a week. At the beginning of Phase II and each month from months 7-18 they will be asked to set a goal of either maintaining weight loss or losing further weight (e.g. choice will be either 0, 0.5 pounds per week, with a default of 0 pounds if nothing is chosen). Inviting people to set more ambitious goals than maintenance is based on evidence that people often voluntarily commit to more ambitious goals than would be economically rational and this commitment can help them achieve those goals.

Each month we will provide each study participant with a graph on the web portal that shows a line beginning at their current weight and dropping to their target weight over the remaining months of Phase I (see Figure 4 in grant proposal, which presents a sample weight loss line for a participant who begins Phase I at 250 lbs and sets a one pound per week weight loss goal over 6 months ideal weight loss trajectory and fresh start trajectory described below.). Participants will self-monitor weights daily. Each morning before eating or drinking and after urinating, participants will weigh themselves and their weights will automatically be transmitted by the Withings Scales to the Way to Health system.

Participants will then receive automated feedback from the system (they may choose text or email) on their progress relative to their goals and their potential earnings, helping to make the payments feel immediate. They will be told that they will receive the full amount if they meet the 6 month target for their weight (the sum of the monthly weight loss goals) but half the money if they do not. Daily monitoring provides participants with a frequent reminder of their goals, chosen because people tend to adopt a narrow frame of reference to diets, rededicating themselves each day. Daily weigh-ins should reduce binge eating by making participants constantly accountable for their weight. Monthly graphical feedback provides encouragement and a symbolic reward for slow and steady progress. Participants in the lottery arm will be eligible for a daily lottery prize with an expected value of \$3.00/day if, prior to resolution of the lottery, they reported a weight at or below their goal on the ideal weight loss trajectory in Figure 4. The lottery provides both infrequent large payoffs (a 1 in 100 chance at a \$100 reward) and frequent small payoffs (a 1 in 5 chance at a \$10 reward) since subjects are motivated by both the future (fixation on large potential winnings) and the past (how often did I win?). Subjects will be assigned a 2-digit number with two distinct digits upon entry into the study, e.g. 27. A two digit random number will be generated for each day. If the last digit includes either a 2 or 7 (a 1 in 5 chance), and the subject reported a weight at or below target weight, s/he wins \$10. If the two digits are 27 (a 1 in 100 chance) the subject wins an additional \$100. When a subject reports a weight above target, we will still generate a 2-digit daily number and tell the subject if s/he would have won the lottery that day if s/he had reported a weight at or below target. We believe that a desire to avoid the regret associated with not winning combined with learning that one would have won, had one been adherent, will motivate participants to a greater degree than only on the value of the rewards. A key aspect of the weight loss trajectory is that it can be reset monthly, a critical feature in the likely event that a participant falls short of attaining a monthly weight loss goal. To avoid discouraging such subjects, who would otherwise suddenly have to lose a lot of weight to get back on track and might decide to drop out of the study, each participant will be given the opportunity for a fresh start. The overall goals set at beginning of Phase I will stay the same, but the slope of the trajectory will adjust (i.e., steepen) such that the participant need not binge diet following a month of poor weight loss performance (see Fresh start trajectory in Figure 3, for a subject who lost 1 lb. instead of 4 lbs. in first month). Keeping the overall weight loss goal constant makes the procedure fair for participants who maintain the ideal trajectory, while adjusting the slope of the weight loss line allows for recovery from slip-ups, an approach we have used to attain minimal lost to follow-up rates of less than 10% in previous weight loss studies. To give participants frequent feedback, we will pay out 50% of winnings to date at the end of each month. To minimize falsification of weights and to utilize the amplification of motivation provided by loss aversion, the other half will be held in a virtual account and paid to participants at the end of each 6-month

period only if they have met or exceeded their monthly goal. The monthly goal will include a two-pound margin to account for the added weight of clothing worn by participants at each 6 month in-person weigh-in. Between months 19-24 (Phase III), participants will not receive incentives tied to weight maintenance to evaluate sustainability of effects achieved in Phases I and II.

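### Section 10.6 sets no maximum slope, so the line drawn at the last Phase I reset asks a participant above baseline for more than the 12 lb in four weeks at which 13.5 calls for slowing down

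*Combined protocol and SAP*

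**What the plan says.** Section 10.6 (Design of the Incentives) contains these rules for Phase I:

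- **Goal.** Incentive participants are "given a weight loss goal for the first 6 months of 0.5 lb a week". The six-month figure is described as the "6 month target for their weight (the sum of the monthly weight loss goals".
- **Line.** A monthly graph "shows a line beginning at their current weight and dropping to their target weight over the remaining months of Phase I".
- **Reset.** After a poor month the participant may have the line redrawn: "The overall goals set at beginning of Phase I will stay the same, but the slope of the trajectory will adjust (i.e., steepen". The stated purpose is that this is done "such that the participant need not binge diet following a month of poor weight loss performance". The reason for not moving the goal is fairness: "Keeping the overall weight loss goal constant makes the procedure fair for participants who maintain the ideal trajectory".
- **Daily eligibility.** A participant can win "if, prior to resolution of the lottery, they reported a weight at or below their goal on the ideal weight loss trajectory". The same section also names two lines, the "ideal weight loss trajectory and fresh start trajectory described below".
- **Held half.** Half of the winnings is paid monthly. The other half is paid at the six-month weigh-in only if the goal is met, with a two-pound allowance for clothing.

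Section 13.5 (Risk/Benefit Assessment) sets the safety levels. Participants whose weight falls by more than 5 lb in one week, 8 lb in two weeks or 12 lb in four weeks are asked to slow down. They are also reminded that faster loss earns no extra incentive.

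**The concern.** A fixed goal, a line that restarts from current weight and a shrinking number of weeks together make the slope grow without limit as Phase I runs out. The only restraint in the text is the qualitative aim of avoiding binge dieting. At the last reset, the pace that keeps a participant eligible for the lottery can therefore be one that 13.5 asks the same participant to reduce.

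The stake is consistency between a payment rule and a safety rule. Section 13.5 rests its low-risk assessment partly on the incentives encouraging gradual loss, and for this subgroup in this month the line does not. The money that depends on the line is modest: at $3.00 a day, at most $84 of expected winnings over 28 eligible days. The half held back from earlier months depends on the six-month target as well.

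**Working it through.** **Inputs.** Goal rate 0.5 lb per week, six months, monthly resets, fixed goal (all 10.6); slow-down levels (13.5). Let w be weeks per month and x the pounds above baseline at the start of month 6.

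**Month length.** The plan gives no definition, but its fresh-start example (a participant who lost 1 lb against a 4 lb target in month one) follows a sample line of one pound per week. 1 × 4 = 4 lb, so the example implies four-week months. The alternative is 26/6 = 4.33 weeks.

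**Plan's own figure.** The lottery's expected value reproduces: 0.01 × $100 + 0.20 × $10 = $3.00 per day.

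**Goal.** 0.5 × 6w: 12 lb for w = 4, and 13 lb for w = 4.33.

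**Last line.** It runs from x above baseline to the full goal below it, in w weeks:

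- Weekly slope = (3w + x)/w = 3 + x/w
- Four-week pace = 12 + 4x/w, which is 12 + x for w = 4 and 12 + 0.92x for w = 4.33

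| x (lb above baseline) | w = 4, 12 lb goal | w = 4.33, 13 lb goal |
|---|---|---|
| 0 | 12.0 | 12.0 |
| 1 | 13.0 | 12.9 |
| 2 | 14.0 | 13.8 |
| 5 | 17.0 | 16.6 |

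Under both conventions the 12 lb level is exceeded when x > 0 and only equalled at x = 0. The two-week level needs 2(3 + x/w) > 8, so x > w: above 4 lb or 4.33 lb.

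**Two-pound margin.** If it were also credited to the line, the four-week pace would be 4(3w + x − 2)/w, which exceeds 12 when x > 2 under either convention.

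**Earlier resets.** With two months left and w = 4, the pace is (12 + x)/2 per four weeks, so the level is crossed only when x > 12. With w = 4.33 it needs x > 13. The conflict is essentially confined to the last reset.

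**If eligibility follows the original line instead.** At the end of month 5 (w = 4) that line is 0.5 × 20 = 10 lb below baseline. A participant at baseline losing 3 lb per week gains on it at 2.5 lb per week and reaches it after 10/2.5 = 4 weeks, when Phase I ends. This reading is steeper, so a cap works only if eligibility is tied to the capped line.

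**Who it can reach.** Two of four equal arms: 344/4 × 2 = 172 people are under the rule. The documents give no basis for the share above baseline at month 5.

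**The case against.** The best reply is that nothing here is compelled. The fresh start is an opportunity, and missing the line only forfeits lottery chances and possibly the held half. Section 13.5 monitors actual loss and applies whatever the line says. A reader might infer that the protocol mandates unsafe weight loss or disables its own safety rule. The documents support neither. What stands is narrower: the two rules can give one participant opposite signals.

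Second, the reset softens the original line, and the binge-dieting aim is illustrated with one poor early month, not five months without net loss. That is right for early resets, where the design works as intended. It does not supply a limit for the last one.

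Third, a reader might infer that a participant exactly at baseline is already over the level. That follows only from combining a 26-week goal (13 lb) with a 28-day final month. With either consistent convention the pace is exactly 12 lb.

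Fourth, the trajectory figures, at least one of which sits in the grant proposal, are not available here and may show a limit. If so, it belongs in the protocol text.

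Finally, a cap at 3 lb per week still allows six times the nominal 0.5 lb per week. True: the cap removes the contradiction with 13.5 but does not make the late line gradual.

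**Conclusion.** The point holds, as a minor one. With no stated maximum slope, the line drawn at the last Phase I reset exceeds the four-week level in 13.5 for any participant above baseline, by x lb with four-week months or 0.92x lb with 4.33-week months. If the two-pound margin also applies to the line, it does so only above +2 lb.

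This rests on three assumptions: a consistent month length, a last reset with one month left, and no limit in the unseen figures. It concerns the incentive and combined arms only. The number affected cannot be derived and is probably small. A reader might go on to infer harm to power or to the primary comparison. Nothing supports that: the 18-month weight outcome, the tests and the sample size do not depend on the slope of this line.

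**What to change.** Add to 10.6: *The fresh-start line will not exceed a slope of 3 lb per week (12 lb per four weeks), and daily lottery eligibility follows this capped line.* The second clause is needed because the current text leaves open which line decides eligibility. Keep the held half tied to the original six-month target with the two-pound margin, which preserves the constant goal and its fairness rationale.

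**Cost.** One sentence and one limit in the platform. The cap changes nothing for participants at or below baseline at the last reset. For those above, the capped line drops 12 lb (13 lb with 4.33-week months) and so ends x lb short of the full goal: 1 lb short at +1 lb, 5 lb short at +5 lb. The held half still rewards reaching the original target. With c lb of clothing, someone who follows the capped line exactly earns it only if x + c ≤ 2. That remaining pull towards faster loss is the price of keeping the goal constant and should be acknowledged.

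Section 11.2 shows that randomization had begun. If Phase I is already complete, what remains is to compare final-month line slopes with the rapid-loss alerts and report the result to the DSMB.
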